4 STUDY DESIGN

This protocol is a single site study. The study will include a baseline 3T MRI session, and two experiments conducted during two sessions of simultaneous TMS, EEG, and cognitive testing (Figure 1). Both experiments will use the same participants to allow for within-subjects comparisons and the order of experiments will be counterbalanced. Participants who miss a session will be rescheduled or replaced (see Recruitment). Participants will make three visits to the lab, a baseline assessment session and two TMS/EEG sessions, for a time commitment of approximately 8 hours. TMS/EEG Session 1 will occur 1-31 days following the baseline visit and TMS/EEG Session 2 will occur 4-31 days following TMS/EEG Session 1 (Figure 1).

Figure 1. Study Design

[figure not shown]
On each TMS/EEG day, participants will undergo EEG recording using a 64-channel elastic cap. During recording, they will complete two blocks of a task, one for each experiment, which differ only in their timing of TMS delivery. Each block consists of 90 study trials of episodic memory encoding (45 trials) and spatial processing (45 trials) for a total of 180 trials (90 memory and 90 spatial processing) per TMS/EEG session (Table 1).

Table 1. Conditions and trial counts.

	Parietal Stimulation				Vertex Stimulation				TOTAL			
	Stim On		Stim Off		Stim On		Stim Off					
	Memory	Spatial	Memory	Spatial	Memory	Spatial	Memory	Spatial				
Experiment 1	30	30	15	15	30	30	15	15	180	360		
Experiment 2	30	30	15	15	30	30	15	15	180			

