TMS will be paired with task trials and consist of 2-second trains of continuous theta burst stimulation (cTBS; see Study Procedures). In Experiment 1, TMS will be delivered during the rest phase immediately prior to trial onsets (Figure 2). In Experiment 2, TMS pulses will occur during the trial while participants are actively engaged in the task (Figure 2). The order of experiments will be counterbalanced across subjects within each session. TMS will be delivered to an episodic memory network-connected location in posterior parietal cortex (see 4.4.2. TMS, below) or to the vertex as an inactive control condition, and the order of stimulation location will be counterbalanced across TMS/EEG sessions. One-third of trials will contain no stimulation as an additional control to examine behavioral and neural effects in the absence of the TMS sensory artifact (Table 1). Participants will then be tested on encoded items, also with EEG recording. EEG data will be examined in an event-related design, with timeseries following trial onsets compared across task (memory encoding, spatial processing, and memory retrieval) and stimulation (parietal-TMS, vertex-TMS, and no-TMS) conditions.

Figure 2. Experiment Design

Recruitment

Healthy participants will be recruited from the pool of individuals self-referring to the study directly and via the NIH Clinical Research Volunteer Program and via advertisements that will be pre-approved by the IRB. Although NIH employees will be allowed to participate, no direct solicitation of employees/staff by supervisors or co-workers will take place. Any recruitment material will be IRB approved. Participants who indicate interest will be pre-screened by phone. Pre-screening questions are listed in Appendix B. IRB-approved ads will be posted on NIH listservs with the permission of the moderator and IRB required statement on how the receiver was identified. Listservs may include NIH sponsored recruitment list serves such as (NIH HV recruitment list serv). Listserv announcement will include:

“You are receiving this message because your email address is included in the above NIH Listserv mailing list. The purpose of this message is to inform you of studies that are recruiting

Abbreviated Title: Task-dependent TMS and memory

Version Date: 11.15.22

volunteers at NIH, Bethesda, Maryland. The moderator of the listserv mailing list has permitted its use for this distribution”.

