Memory Task: This is a test of episodic memory, including item recognition and context recollection^{30,52,53}. In the task, participants will be shown a series of objects in one of four quadrants on the screen. They will be instructed to remember the objects and where they were located, both of which will be tested later. To ensure attention and for consistency with the spatial task (see below), they will be asked to indicate by button press whether the object is primarily used outdoors (e.g., a baseball) or indoors (e.g., a television). During the encoding phase, each object will be presented for 4 seconds with 4 seconds between trials. In Experiment 1, TMS will occur during a 2 second cue before each trial and in Experiment 2, TMS will occur in the first 2 seconds of stimulus object presentation. There will be 180 encoding trials, interspersed with 180 trials of the spatial task (described below). Trial order will be randomized. The retrieval phase will occur following the end of encoding. Participants will be shown, sequentially and in randomized order, the 180 encoded objects and 180 new lure objects, for a total of 360 trials. For all trials, they will respond with whether the object was old (previously seen) or new (not previously seen) and their confidence on a scale of 1-6 (1=confident new,

Abbreviated Title: Task-dependent TMS and memory

Version Date: 11.15.22

6=confident old) as a measure of item recognition. If the object was previously seen, participants will then be asked which quadrant the item was presented in to provide a measure of context recollection. We will use two different versions of the task with different and non-overlapping sets of objects at the two test sessions and the order of versions will be counterbalanced across participants.

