Spatial Task: This is a test of spatial processing, which will serve as a control task to isolate neural markers of memory engagement, versus engagement in any task with similar visuospatial qualities. Notably, spatial processing activates a network of frontoparietal including the posterior parietal cortex regions^{54,55}, allowing it to further serve as a control to isolate hippocampal network effects of TMS from the local effects of TMS on the stimulated region. In each trial of this task, participants will be shown an arrow pointing to one corner of the screen and displayed in one of four quadrants. They will be instructed to indicate by button press whether the arrow points to the corner in which it is displayed (“match,” e.g. pointing to the upper right corner in the upper right quadrant) or a different corner (“no-match,” e.g. pointing to the upper right corner in the upper left quadrant). Accuracy of match/no-match responses will be assessed. Each arrow will be presented for 4 seconds with 4 seconds between trials. In Experiment 1, TMS will occur during a 2 second cue before each trial and in Experiment 2, TMS will occur in the first 2 seconds of stimulus presentation. There will be 180 trials, interspersed with encoding trials of the memory task. We will use two different versions of the task at the two test sessions.

TMS

The parietal target will be the region of the left posterior parietal cortex with the greatest connectivity with the left hippocampus derived from the baseline resting-state fMRI session³¹. This region was chosen because of its dense connections with the hippocampus^{56,57}. Thus, stimulation of this location can modulate function of the hippocampal-cortical network^{30-36,38}.

The control target will be vertex, a commonly used active control site which does not influence neural or behavioral activity⁵⁸.

TMS targets will be marked in the participant’s anatomical MRI volume and located with a frameless stereotaxic system. If any experiment, for any reason, fails to produce useful individual targets, a literature-based location for the parietal cortex³¹ will be used as our location of stimulation. To reduce the influence of diurnal variations in the responsiveness to neuroplasticity protocols⁵⁹, we will make every effort to test subjects during the same time of day.

[figure not shown]

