8.3.2 Analysis of the Primary Endpoints

- Primary Endpoint 1: Investigate how TMS modulates EEG neural measures of successful memory and the relevance of modulation to behavioral performance
This aim will examine behavioral and EEG neural outcome measures (Primary Endpoints 1-4). We will perform 3x3 ANOVAs on each outcome measure with the factors trial type (successful/ unsuccessful/ spatial), stimulation site (parietal/ vertex/ none), and their interaction. We will particularly focus on the main effect of stimulation site to determine

the influence of parietal-TMS on memory performance and its neural correlates, and the interaction effect to determine the task specificity of TMS effects. Thresholds for significant effects will be set at $p<0.025$ following FDR correction for multiple comparisons.

- Primary Endpoint 2: Examine how memory task state influences susceptibility to plasticity via TMS and determine the optimal neural state for improving memory
This aim will examine behavioral and EEG neural outcome measures (Primary Endpoints 1-4). We will perform 3x3x2 ANOVAs on each outcome measure with the factors trial type (successful/ unsuccessful/ spatial), stimulation site (parietal/ vertex/ none), stimulation timing (pre-trial and mid-trial) and their interaction. We will particularly focus on the interaction effect of stimulation site and timing to determine the influence of memory task-state parietal-TMS on memory performance and its neural correlates, and the three-way interaction effect to determine the task specificity of state-dependent TMS effects. Thresholds for significant effects will be set at $p<0.025$ following FDR correction for multiple comparisons.

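### The protocol does not say whether a participant keeps one experiment order in both sessions, and the Objective 2 model has no block-position term; if orders differ, the site × timing contrast loses precision

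*Combined protocol and SAP*

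**What the plan says.** - **Blocks and sites (section 4, Study Design, and Table 1).** A session has two blocks, one per experiment, which differ only in when TMS is delivered. A block has 90 study trials, 45 memory and 45 spatial. One site is stimulated per session. Table 1 gives 30 stimulated and 15 unstimulated memory trials for each site and experiment.
- **Order (section 4).** "The order of experiments will be counterbalanced across subjects within each session". Site order is counterbalanced across sessions. Nothing relates a participant's experiment order in the second session to that in the first.
- **Timing of trials (section 4, Behavioral Tasks).** For memory trials, "each object will be presented for 4 seconds with 4 seconds between trials". For spatial trials, "Each arrow will be presented for 4 seconds with 4 seconds between trials". Also: "In Experiment 1, TMS will occur during a 2 second cue before each trial".
- **Testing (same place).** "The retrieval phase will occur following the end of encoding", and "Participants will be shown, sequentially and in randomized order, the 180 encoded objects and 180 new lure objects".
- **Analysis (section 8.3.2).** Objective 2 uses a 3×3×2 ANOVA with trial type, stimulation site, stimulation timing and their interaction. "We will particularly focus on the interaction effect of stimulation site and timing". No term for block position or experiment order is listed.

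**The concern.** Within a session, stimulation timing coincides with block position: whichever experiment runs first supplies the objects studied earlier. If all objects are tested together at the end, first-block objects have a longer lag and more intervening material, so they may be remembered less well. Fatigue or practice over the session could act in the same place.

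Objective 2 turns on whether the mid-trial minus pre-trial difference is larger with parietal than with vertex stimulation. For each participant this is a double difference across two sessions. A position effect drops out if the two sessions share an order, and does not if they differ. The plan leaves open which applies, and its model has no term to absorb the effect. What is at stake is the precision of the focal memory contrast, which rests on cells of 30 stimulated trials.

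**Working it through.** **1. The plan's own figures.** Table 1: 30 + 30 + 15 + 15 = 90 trials per site and experiment, which is one block. Four blocks give the stated 360. The 180 encoded objects under Behavioral Tasks agree with this only as a total over both sessions (4 × 45 = 180). The sample size of 32 (section 8.2) can be reproduced with η² = 0.28, f² = 0.28/0.72 = 0.389, α = 0.025, power 0.80, a three-level within-subject factor (df 2 and 2(N − 1)) and λ = N·f². Section 8.2 does not state those options, so the match depends on that choice. The figure contains no position component and does not depend on this point.

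**2. Lag difference.** With random test order, the mean lag difference is the distance between block midpoints, which is one block length if there is no break.
- 90 × (4 + 4) s = 720 s = 12 min, with 45 more memory objects in between.
- If the 2 s cue is added to the 4 s gap in both blocks: 90 × 10 s = 900 s = 15 min.

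**3. How position enters the contrast.** Let b be the advantage of one block position over the other, additive and equal across sites and sessions. Let s = +1 or −1 show which position the mid-trial block takes in a session. The contrast is

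C = (parietal mid − parietal pre) − (vertex mid − vertex pre),

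and position contributes (s_P − s_V)·b.
- Same order in both sessions: 0 for everyone. Added variance 0.
- Orders independent: 0 for half of participants, ±2b for the rest. Added variance ½ × (2b)² = 2b².
- Order always reversed: ±2b for everyone. Added variance 4b².

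With each session balanced 16:16, the mean contribution is 0 in all three cases.

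**4. Size.** The documents give neither accuracy nor b. Assume 60% accuracy, all 30 trials per cell scored and binomial variance only: 4 × 0.6 × 0.4/30 = 0.032, or 320 squared percentage points. Effective N is 32 divided by (1 + added share).

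| b (points) | Independent: added variance | Effective N | Reversed: added variance | Effective N |
|---|---|---|---|---|
| 2 | 8/320 = 2.5% | 31 | 16/320 = 5% | 30 |
| 3 | 18/320 = 6% | 30 | 36/320 = 11% | 29 |
| 5 | 50/320 = 16% | 28 | 100/320 = 31% | 24 |
| 8 | 128/320 = 40% | 23 | 256/320 = 80% | 18 |

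**5. In terms of power.** Take a one-df contrast with 80% power in the absence of position error (N = 32, two-sided α = 0.025).
- Contrast SD 18.3 points (binomial floor at 50% accuracy): b = 2 gives 79% (independent) or 78% (reversed); b = 5 gives 74% or 68%.
- Contrast SD 25 points, allowing for between-person variation: b = 5 gives 77% or 73%.

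**6. Sensitivity to scoring.** The quadrant question follows only for objects judged previously seen. If context recollection is scored on those objects, and 70% are recognised (an assumption), each cell has 21 trials. The baseline is then 4 × 0.24/21 = 457 squared points, and b = 5 adds 50/457 = 11% instead of 16%.

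**The case against.** The strongest reply is that the counterbalancing rule is met in full if half the participants run Experiment 1 first in both sessions and half run Experiment 2 first. Under that list an additive position effect cancels. A reader might infer that balancing across subjects within a session by itself puts error into the site × timing contrast, or biases it. The documents support neither: error arises only if a participant's orders differ, and the average effect is zero under any balanced list. This stands, and it limits the point to something left unspecified.

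Other replies stand in part.
- A single retrieval phase after both blocks is the natural reading but is not spelled out. Section 5.6 allows for a participant with data from one experiment only, and the design figures are not available here. If testing followed each block, the 12-minute difference would vanish.
- The baseline variance is a floor, so the percentages lean high.
- Cancellation is exact only if b is the same for both sites and sessions. Section 2.2 reports effects of single cTBS sessions, so carry-over from a parietal first block could differ from that of a vertex first block. A fixed order would not remove this.
- Reversing the order balances timing within each participant, which a fixed order gives up. However, no hypothesis in section 8.1 rests on the timing main effect. Objective 2a also compares mid-trial with pre-trial parietal stimulation, but that comparison lies within one session and carries ±b under every scheme. It therefore does not favour reversal.

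**Conclusion.** The point holds as a conditional loss of precision. Three allocation lists, all compatible with section 4, give the focal Objective 2 contrast an added variance of 0, 2b² or 4b², and the plan neither chooses among them nor models position.

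The size depends on assumptions: one retrieval phase after both blocks, an additive b, 60% accuracy and no variance beyond binomial. On these, b of 3 to 8 points adds about 6–40% with independent orders and 11–80% with reversed orders. These are upper-end figures, because between-person variation or scoring only recognised objects lowers them. The effective N of 18 needs an 8-point effect, every participant reversed and purely binomial variance together. At 2 points the loss is one or two points of power. The matter merits a change because the remedy is a single allocation rule.

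**What to change.** In section 4, state that each participant has the same experiment order in both TMS/EEG sessions, with half of participants in each order, crossed with site order and task-version order. Say there too that one retrieval phase follows both blocks, if that is the intention.

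If orders have already been allocated, add block position (experiment order) to the Objective 2 model in section 8.3.2. Order is known for every participant, so this removes an additive effect for about one degree of freedom.

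The allocation rule costs no visits, time or participants. Its downside is that the timing main effect is then balanced only between participants: averaged over sites, it carries position variance b², against b²/2 with independent orders and 0 with reversed orders. A position effect that differs by site or session is not removed.

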1 PROTOCOL SUMMARY

1.1 SYNOPSIS

Title:	Task-dependent effects of TMS on the neural biomarkers of episodic memory
Study Description:	The Behavioral Neurology Unit studies the human brain systems underlying learning and adaptation with the goal of finding interventions to make these processes more efficient. In this study, we are interested in examining how the task state of the episodic memory network influences the effect of facilitatory TMS on memory and its EEG neural correlates. It is hypothesized that Network-targeted parietal-TMS will improve memory performance and enhance EEG biomarkers of successful memory performance, but that these changes will be modulated by the ongoing task activity during stimulation.
Objectives:	
Primary Objectives:
 
 Investigate how TMS modulates EEG neural measures of successful memory and the association of this modulation with behavioral performance Examine how memory task state influences susceptibility to plasticity via TMS and determine the optimal neural state for improving memory 
Exploratory Objectives:
 
 Search for MRI predictors of the effects of TMS
Endpoints:	
 Primary Endpoints: Memory performance, Late Positive Posterior ERP, evoked theta/alpha power (secondary), EEG functional connectivity (secondary) Exploratory Endpoints: fMRI resting state functional connectivity, fractional anisotropy
Study Population:	32 Healthy Volunteers ages 18-40. Referrals will occur from the NIH Clinical Research Volunteer program or through self-referrals to the protocol.
Description of Sites/Facilities:	Protocol activities will occur at the OP5 clinic and 7SW clinic at the NIH clinical center.
Enrolling Participants:	50 Healthy Volunteers ages 18-40

Abbreviated Title: Task-dependent TMS and memory

Version Date: 11.15.22

Study Duration: 60 months

Participant Duration: 1 month

Abbreviated Title: Task-dependent TMS and memory
Version Date: 11.15.22

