2.2 BACKGROUND

Episodic memory provides a means by which we reflect on the past, make decisions about the future, and form a learned identity. Deficits in this system occur in a variety of neurological and psychiatric disorders¹⁻⁵, making them one of the most debilitating problems in neurology^{6,7}. However, there currently exist no effective treatments for memory impairment. A better understanding of how the brain adapts to perform a memory demand will not only expand our basic knowledge of memory processing but could inform novel treatments for individuals with memory impairments.

Episodic memory depends on the hippocampus^{8,9} and a distributed set of regions which form the hippocampal-cortical network (HCN), including medial prefrontal, posterior cingulate, and medial and lateral parieto-occipital cortex¹⁰⁻¹³. This network shows changes in fMRI activity and connectivity in response to successful memory encoding and retrieval¹⁴⁻¹⁸. Likewise, abnormal function of this network has been associated with memory impairment in many disorders, including traumatic brain injury^{19,20}, epilepsy^{21,22}, and Alzheimer's disease^{23,24}. Additionally, the HCN generates real-time EEG signatures of successful encoding and retrieval, most notably the Late Positive Posterior Event-Related Potential (ERP)²⁵ and oscillatory activity in the theta/alpha band²⁶.

There has been substantial recent interest in using brain stimulation to manipulate brain networks, both to test the role of particular regions and networks in memory processing causally and as a potential therapeutic tool in treating memory disorders²⁷⁻²⁹. Noninvasive transcranial magnetic stimulation (TMS) has been used to manipulate activity and connectivity in the HCN and improve memory performance in healthy adults³⁰⁻³⁹. Repeated treatment over days produces

Abbreviated Title: Task-dependent TMS and memory

Version Date: 11.15.22

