3 OBJECTIVES AND ENDPOINTS

OBJECTIVES	ENDPOINTS	JUSTIFICATION FOR ENDPOINTS
Primary		
1. Investigate how TMS modulates EEG	1. Memory performance	1. Memory performance measures will allow us to

[figure not shown]
OBJECTIVES	ENDPOINTS	JUSTIFICATION FOR ENDPOINTS

neural measures of successful memory and the association of this modulation with behavioral performance
 
2. Examine how memory task state influences susceptibility to plasticity via TMS and determine the optimal neural state for improving memory
	
 • Accuracy: Percentage of successful (later remembered hit and correct rejection) vs unsuccessful (forgotten miss and false alarm) trials for item recognition (remember/familiar/new) and context recollection (spatial location) • d': Analysis of hits (correctly remembered as encoded) relative to false alarms (new objects labelled as encoded) for item recognition 
2. Late positive posterior ERP
 
 • ERP amplitude 500-700 ms after trial onset (encoding and retrieval) over parietal and occipital electrodes 
3. Theta/alpha power (secondary)
 
 • Power in the 4-13 Hz band 0-1000 ms after trial onset (encoding and retrieval) 
4. EEG functional connectivity (secondary)
 
 • Pearson correlation coefficients (r) between electrode time courses after trial onset (encoding and retrieval) 	
examine the effects of TMS on performance, as well as to sort successful vs unsuccessful trials for EEG analyses
 
2. The late positive posterior ERP has been previously shown to be a robust marker of successful memory performance²⁵
 
3. Task-induced changes in this frequency band have been previously associated with successful memory performance²⁶
 
4. fMRI functional connectivity modulation via network-targeted TMS has been previously associated with TMS-induced memory improvement. Whether EEG functional connectivity will be similarly altered, and the relevance to memory changes, remains unknown

Tertiary/Exploratory		
1. Search for MRI predictors of the	1. Baseline fMRI functional connectivity	It is hypothesized that TMS influences downstream targets

OBJECTIVES	ENDPOINTS	JUSTIFICATION FOR ENDPOINTS

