Stimulation will be delivered during the encoding phase of the behavioral task, either prior to trial onset (Experiment 1) or simultaneously with trial onset (Experiment 2; see 4.4.1 Behavioral Tasks for timing) in the form of 2-seconds of theta-burst stimulation (50 Hz pulse triplets every 200 ms; Figure 3) at 80% of the motor evoked potential threshold of the right abductor pollicis brevis muscle or 44% of maximum stimulator output, whichever is lower. This protocol has been

Abbreviated Title: Task-dependent TMS and memory

Version Date: 11.15.22

shown previously to particularly influence the hippocampal-cortical network and memory performance³⁷⁻³⁹.

Figure 3. Theta-burst stimulation.

EEG

Participants will be fitted with a 64-channel elastic EEG cap for the duration of each experiment session. Data will be recorded continuously during the study and test phases of the behavioral experiment. The EEG signal will be amplified online, filtered, and digitized continuously along with stimulus onset codes used for subsequent analysis. Independent component analysis and/or other processing techniques will be performed to isolate and remove recurring artifacts from the signal.

Single-trial waveforms will be screened for artifactual contamination. Trials will then be divided based on task type (spatial, memory encoding, accuracy of item recall (memory task) and spatial task performance. The timeseries from trials of the same type and/or accuracy will then be averaged, and the resulting waveforms will be compared across categories. For theta/alpha band analysis, we will additionally use time-frequency decomposition of the event-related averages.

MRI

We estimate a maximum of 1 hour for baseline scanning. Because scanner malfunctions and subsequent loss of data are common, we will not report these as unexpected problems.

Participants whose data are lost due to scanner malfunctions will be rescheduled, if possible.

Participants whose MRI sessions cannot be completed may enter the experiment if the MPRAGE (see below) data have been acquired. They will be rescheduled for the other scans when possible.

MRI anatomical scanning: All participants will have anatomical (MPRAGE) scans at baseline. Participants who have not had one in the past year will receive a standard clinical MRI scan of the head, which will be submitted to the Diagnostic Radiology Department CC for interpretation. Depending on the requirement for a clinical scan, this phase will take 10-30 min.

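### Theta/alpha power is computed from averaged waveforms and so measures essentially evoked power only, although most of the plan describes theta/alpha activity without that limit; single-trial total power should be added.

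*Combined protocol and SAP*

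**What the plan says.** The EEG paragraphs of Section 4 screen single trials for artifact and sort them by task and accuracy. Then "The timeseries from trials of the same type and/or accuracy will then be averaged, and the resulting waveforms will be compared across categories". The theta/alpha measure is built on those averages: "For theta/alpha band analysis, we will additionally use time-frequency decomposition of the event-related averages". No section describes decomposing single trials.

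The measure is described differently in different places:

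- Section 1.1 (Synopsis) lists it as "evoked theta/alpha power (secondary".
- Section 3 defines it as "Power in the 4-13 Hz band 0-1000 ms after trial onset (encoding and retrieval", without saying evoked, induced or total, and justifies it thus: "Task-induced changes in this frequency band have been previously associated with successful memory performance".
- Section 2.2 places "oscillatory activity in the theta/alpha band" beside the late positive ERP as a signature of encoding and retrieval.
- The hypotheses in Sections 4 and 8.1 refer simply to theta power.

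Hypothesis 1b in Section 8.1 compares parietal with vertex stimulation on successful relative to unsuccessful trials. Hypothesis 1d correlates the EEG effects with memory improvement. Section 8.3.2 makes successful/unsuccessful/spatial a factor in every ANOVA.

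On trial numbers, Section 4 states: "Each block consists of 90 study trials of episodic memory encoding (45 trials) and spatial processing (45 trials". Table 1 divides the 45 memory trials per site and experiment into 30 with stimulation and 15 without.

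**The concern.** Averaging in the time domain cancels activity whose phase varies from trial to trial. A spectrum computed afterwards describes what is locked to onset, plus a small leftover from incomplete cancellation. Two things are at stake.

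First, if parietal stimulation raised theta/alpha activity that is not phase-locked, the measure would register little of it. A null result could then be read as evidence against an effect on theta power in general, because the hypotheses carry no restriction to evoked power.

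Second, the leftover shrinks with the number of trials averaged. Successful and unsuccessful cells will rarely be equal in size, so the contrast in hypothesis 1b includes a difference that reflects trial counts and not physiology. Those counts depend on memory accuracy, so the distortion can carry into the correlation in hypothesis 1d.

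**Working it through.** The plan states no figure for retained power, so there is none to reproduce.

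**Inputs.** Table 1 gives 30 stimulated memory trials per site and experiment. If the 3x3 ANOVA of Section 8.3.2, which has no timing factor, pools the two experiments, n is up to 60. Sorting by accuracy makes cells smaller; n = 10 and n = 20 are used as illustrations. R is not in the documents and is taken from 0 (the extreme case) to 0.9.

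**Step 1: power kept by averaging.** Share of single-trial power in an n-trial average = R² + (1 − R²)/n.

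- R = 0: 1/30 = 3.3%; 1/60 = 1.7%; 1/10 = 10%.
- R = 0.3, n = 30: 0.09 + 0.91/30 = 12%.
- R = 0.5, n = 30: 0.25 + 0.75/30 = 28%.
- R = 0.9, n = 30: 0.81 + 0.19/30 = 82%.

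A simulation at R = 0 (6 Hz burst of random phase, 5-cycle Morlet wavelets, 4–13 Hz, 0–1000 ms, 150 runs per n) kept 3.7% at n = 30, 1.9% at n = 60 and 9.4% at n = 10, in line with 1/n.

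**Step 2: sensitivity to a non-phase-locked change.** Assume a 20% rise in the non-phase-locked part, which is (1 − R²) of single-trial power. Total power rises by 0.2(1 − R²). Evoked power at n = 30 rises by 0.2(1 − R²)/30, relative to the Step 1 value.

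| R | Rise in total power | Relative rise in evoked power |
|---|---|---|
| 0 | 20% | (0.2/30)/0.0333 = 20% |
| 0.3 | 0.2 × 0.91 = 18.2% | (0.182/30)/0.1203 = 5.0% |
| 0.5 | 0.2 × 0.75 = 15% | (0.15/30)/0.275 = 1.8% |
| 0.9 | 0.2 × 0.19 = 3.8% | (0.038/30)/0.8163 = 0.2% |

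The denominator matters. At R = 0 the expected evoked value still rises by 20%, but from a residual of only 3.3% of single-trial power (an absolute rise of 0.2/30 = 0.7%). Once any phase-locked part is present, it dilutes the change.

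**Step 3: unequal cells.** The residual is (1 − R²)/n. With an assumed 20 successful and 10 unsuccessful trials out of 30:

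- R = 0: 1/20 = 5% against 1/10 = 10%, a difference of −5% of single-trial power with no physiological difference.
- R = 0.5: 0.75 × (−5%) = −3.75%.
- R = 0.9: 0.19 × (−5%) = −0.95%.

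If accuracy also differs by site, the bias enters the site comparison. Assume 20 of 30 successful at vertex and 24 of 30 at parietal, with R = 0. Vertex gives 1/20 − 1/10 = −5%, and parietal gives 1/24 − 1/6 = −12.5%. The spurious site-by-success effect is −7.5%, opposite in direction to hypothesis 1b. The expected mean of single-trial power does not depend on n, so total power has no such residual.

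**Step 4: overlap with the ERP endpoint.** Section 3 defines that endpoint as "ERP amplitude 500-700 ms after trial onset (encoding and retrieval) over parietal and occipital electrodes". A 200 ms mean passes |sin(π·f·0.2)/(π·f·0.2)| of the amplitude of a sinusoid at f Hz. Over whole frequencies from 4 to 13 Hz the largest value is 23% (at 4 Hz), and it is 0 at 5 and 10 Hz. A slow Gaussian positivity (assumed SD 80–200 ms) has under 0.5% of its energy in the band.

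**The case against.** The strongest reply is that the synopsis names evoked power, and decomposing the event-related average is the ordinary way to obtain it. On that reading the method is a deliberate choice and the other sections merely drop an adjective. Task-induced may mean no more than caused by the task, since the same table uses induced in that loose sense for the memory gain from TMS. Whether the study cited in support used single-trial power cannot be seen from the documents. The measure is secondary in Sections 1.1 and 3 and exploratory under Objective 2. Section 8.2 shares alpha only between memory performance and the late positive ERP.

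Much of this stands. Evoked power is a legitimate measure, and making ERP-subtracted power the endpoint would discard genuine onset-locked responses. What remains is that the hypotheses are worded more widely than the measure, that Section 8.1 numbers it Primary Endpoint 3, and that the trial-count residual affects evoked power even if evoked power is what was meant.

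A reader might also infer three stronger things that the documents do not support:

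- *That the measure largely repeats Primary Endpoint 2.* Both come from the same averaged waveform, but the 500–700 ms mean is nearly insensitive to 4–13 Hz.
- *That a change in the late positivity alone would appear as a theta/alpha change.* A slow positivity puts almost no energy in the band. A sharper deflection would put in more, but nothing in the plan shows that one is expected.
- *That the measure cannot test the oscillation at all.* That would need R = 0 throughout; phase-locked or phase-reset activity survives averaging.

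**Conclusion.** The concern holds in a limited form. As specified, theta/alpha power is evoked power. It agrees with the synopsis label but not with the unrestricted wording in Sections 2.2, 3 and 8.1 and the Section 4 hypotheses. Averaging keeps 1.7% to 3.3% of non-phase-locked power for 60 to 30 trials, and 10% for a cell of 10. Phase-locked effects can still be tested.

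The residual also biases the successful-versus-unsuccessful contrast when counts differ: by 5% of single-trial power at R = 0 with 20 and 10 trials, falling to about 1% at R = 0.9. These sizes rest on assumed accuracy and an assumed range for R. The 1/n rule itself needs only independent random phases.

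This is an inexpensive improvement to a supporting endpoint. It does not threaten memory performance or the late positive ERP.

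**What to change.** In the EEG part of Section 4:

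- Add that each artifact-free trial will be decomposed and power then averaged across trials (total power), and use this to test the theta/alpha hypotheses.
- Keep evoked power as a separately labelled measure, with trial counts matched between successful and unsuccessful cells.
- Report power after subtracting the condition ERP from each trial only as a supplement.
- Use the label evoked or total consistently in Sections 1.1, 3, 4 (hypotheses) and 8.1.

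The cost is plan wording and computing time, on the same recordings and with the single-trial screening already planned. There are three downsides. Single-trial power is more exposed to residual artifact. Matching discards trials from the larger cell, for example 10 of 20 when the other cell has 10. In Experiment 2, bursts every 200 ms (1/0.2 s = 5 Hz) run through the 0–1000 ms window, so stimulation-locked signal lies in the band for both evoked and total power. Adding total power does not remove that problem.
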